## 1.2 Overview of Study Design

The study design is heavily predicated on the designs used for IFPS-1 and FDA IFPS- II which are the two major previous longitudinal feeding practice studies. Building on the past longitudinal work maximizes the comparability between current study data and past work which facilitates assessing changes over time. We have also utilized aspects of the Feeding Infants and Toddlers Study (FITS) to address nutrition and feeding practices of toddlers. Additionally, we leverage many of the approaches previously used, such as rotating question modules, to ensure study efficiency. At the same time, we use some alternative approaches, such as onsite-recruiting of participants, to address challenges that occurred in the past. The current study also has a broader scope than the past longitudinal work in that it includes both infant and toddler feeding practices through 24 months and addresses new issues that have emerged such as the precursors to early childhood obesity.

Our study is a hybrid design, incorporating a core longitudinal sample (the “core” sample) and a supplemental cross-sectional sample (the “supplemental” sample) to ensure precision in estimates at key time points. The core longitudinal sample of women and their infants will be enrolled in the study as they enroll in WIC (either prenatally or before their infant is 2.5 months old if they did not enroll prenatally). They will be followed until the infants are 24 months old, with up to 11 interviews occurring prenatally, and at 1, 3, 5, 7, 9, 11, 13, 15, 18, and 24 months. The supplemental cross-sectional sample will also be recruited as the women and their infants enroll in WIC. This sample will be interviewed at four key time periods (1 or 3, 7, 13, and 24 months). We will collect birth hospital records and WIC record data at 7, 13, and 24 months for both samples. Concurrent with the start of WIC participant data collection, we will also collect data on WIC program features and personnel through a survey of WIC service site staff and key informant interviews at the State and Local levels.

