introduced the study, the helper will call a Westat number to make contact with a Westat telephone recruiter who will assign the woman to the appropriate sample.

5. **Administer Screener.** Westat recruiters (in-person or telephone) will administer the recruitment screener. In sites where the helper calls into the Westat telephone center to connect with a telephone recruiter, we will minimize wait time by monitoring call volume hourly during peak enrollment periods to ensure that all calls are picked up and linked with an interviewer immediately. When needed, we will be prepared to make adjustments to both the number of available toll-free staff and responsible interviewers.

The recruiter will confirm that the woman is eligible (i.e., has not been previously enrolled in WIC for her current pregnancy or that the infant is less than 2.5 months). Eligible respondents will be asked about their race, ethnicity, trimester of enrollment, pre-pregnancy BMI, household composition, and income. Core group participants will be retained irrespective of their responses to these questions. Participants assigned to the supplemental group may be found ineligible at this stage depending on their responses. Only rare population subdomains such as black mothers and infant who have no prenatal WIC exposure will be eligible for the supplemental group. Participants still eligible will also be asked questions to determine whether they plan to stay in the area during the study period, whether they are or will be the caregiver of the WIC infant, and their age. In addition, the interviewer will explain what participation involves; the number and types of interviews to be completed; and the incentive structure.

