**Table 4-1. Interview events for core and supplemental sample**

WIC enrollment	INTERVIEW											
	Infant										Toddler	
	Enrollment	Prenatal	1 month	3 months	5 months	7 months	9 months	11 months	13 months	15 months	18 months	24 months
Core Sample – Prenatal	✓	✓	✓	✓	✓	✓	✓	✓	✓	✓	✓	✓
Core Sample – Infant <6 wks	✓		✓	✓	✓	✓	✓	✓	✓	✓	✓	✓
Core Sample – infant 6 wks-2.5 mos				✓	✓	✓	✓	✓	✓	✓	✓	✓
Supplemental Sample – Prenatal	✓		✓			✓			✓			✓
Supplemental Sample – Infant <6 wks	✓		✓			✓			✓			✓
Supplement Sample – Infant 6 wks-2.5 mos				✓		✓			✓			✓

We will conduct the telephone interviews in English and Spanish and participants will be paid a \$20 incentive on completion of each interview. All post-birth interviews will include a 24-hour dietary recall using the AMPM. Participants will receive a package of measuring guides to help them report

their child's portion sizes during the interview. We will collect replicate intakes on a 10 percent subsample of toddlers at 13, 15, 18, and 24 months in order to estimate "usual" intake.

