#### **Weights**

Table 6-1 shows a planned set of weights. In addition to the cross-sectional weight for each wave, we will create some longitudinal weights for analyses that require analysis of linked data across waves. We note that simple change estimates (as in the percent still breastfeeding) do not require linked data. These change estimates will be prepared by forming point estimates for each wave with

---

 Respondents get the full interview for the month in which they are doing an interview, regardless of missed interviews or which sample they are in (core or supplemental). So questions that require reporting a “date” (e.g., cessation of breastfeeding, introduction of formula, or introduction of supplemental foods) will be asked at every applicable interview until the mother gives us a date or until the question is no longer part of the interviews.

Table 6-1. Weights to be prepared and delivered

Weight name	Core only or combined?	Positive for respondents at which waves?	Additional notes
PrenatalWgt	Core only	Prenatal	
Month1CoreWgt	Core only	1-mo	Only prenatally recruited infants and infants recruited postnatally within the window for the 1-mo interview
Month1CombWgt	Combined	1-mo	Only prenatally recruited infants and infants recruited postnatally within the window for the 1-mo interview
Month3CoreWgt	Core only	3-mo	
Month5CoreWgt	Core only	5-mo	
Month7CoreWgt	Core only	7-mo	
Month7CombWgt	Combined	7-mo	
Month9CoreWgt	Core only	9-mo	
Month11CoreWgt	Core only	11-mo	
Month13CoreWgt	Core only	13-mo	
Month13CombWgt	Combined	13-mo	
Month15CoreWgt	Core only	15-mo	
Month18CoreWgt	Core only	18-mo	
Month24CoreWgt	Core only	24-mo	
Month24CombWgt	Combined	24-mo	
HazardModelCoreWgt	Core only	Prenatal + 1-mo or 3-mo if postnatally recruited	Good for modeling hazard of weaning & introduction of various foods; also good for modeling of BF initiation
HazardModelCombWgt	Combined	At least one postnatal interview	Good for modeling introduction of various foods. Earliest weight that uses entire sample. Larger sample size than HazardModelCoreWgt but can't be used in conjunction w/prenatal data.
InfantCoreLongWgt	Core only	Responded every wave from birth through 13 mo.	Good for growth curve modeling of calories/other variables measured each wave. No plans for analysis, but would be expected by many users on a RUF.

Table 6-1. Weights to be prepared and delivered (continued)

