Weight name	Core only or combined?	Positive for respondents at which waves?	Additional notes
ToddCoreLongWgt	Core only	Responded every wave from birth forward	Good for growth curve modeling of calories or other variables that are measured each wave. No plans to use in our analysis, but would be expected by many users on a RUF.
CritWaveLongWgt	Combined	1/3, 7, 13, 24	If prenatally recruited or recruited postnatally within the 1-mo interview window, responded at mos. 1, 7, 13, and 24. If postnatally recruited, after the 1-mo interview window responded at mos. 3, 7, 13, and 24. Good for growth curve modeling with procedures that cannot handle missed waves.

the wave-specific cross-sectional weight and then subtracting the two estimates at the macro level to get estimates of net change.

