Figure: Percentage of all WIC mothers still breast-feeding, by age of the infant and whether the mother reports knowing about the special WIC food package for breastfeeding women who do not accept infant formula for WIC (Months 1-13)	IFPS-1 p166	Both
Table: Frequency of top 10 reasons women stop breastfeeding within the first 2 and 6 weeks (Cumulative; Months 1, 3)	New	Both
Table: Frequency of top 5 reasons women stop breastfeeding within the first 6 weeks by infant health status and household demographics (Cumulative; Months 1, 3)	New	Both
Table: Frequency of top 5 reasons women stop breastfeeding by the magnitude of the difference between intended and actual breastfeeding duration	New	Both
Table: Percentage distribution of reasons for stopping breastfeeding between 2-3and 4-6 months (Months 3, 5,7)	New	Both
Table: Average Edinburgh Postpartum Depression Scale score by breastfeeding status (Month 3 )	New	Both
Table: Characteristics and circumstances of mothers breastfeeding (Months 1, 7)	New	Both
Table: (Model) Relative risks estimated by the multivariate models of rates of breastfeeding cessation (survival analysis) (Months 1-13)	IFPS-1 p168p168	Both
Figure: Percentage of WIC mothers still breastfeeding by age of the infant and reported receipt of none, one, two, or three WIC program components that support breastfeeding (Months 1-13)	IFPS-1 p173	Both

Table 7-2. Summary of analyses to be conducted (continued)

Table/Figure (Interview months)	Source	Sample
Initiation of Supplemental Foods: The Transitional Phase of Infant Feeding		
Table: Infant feeding patterns of WIC participants (by milk/food category) (Months 3-11)	FITSd S74	Both
Figure: Percentage of WIC mothers who have not yet initiated cereals, fruits, vegetables, and meats at each age of the infant (Months 1-13)	IFPS-1 p186	Both
Figure: Percentage of WIC mothers who have not yet initiated dairy foods, high-protein foods other than meats, and sweet/snack foods, at each age of the infant (Months 1-13)	IFPS-1 p188	Both
Table: Median age of the infant (in weeks) when specific supplemental foods are initiated by selected socio-demographic characteristics of the mother (Cumulative; Months 1-13)	IFPS-1 p189	Both
Table: Percentage of infants and toddlers consuming different types of milk and other beverages by age (Months 3-24)	FITS S40	Both
Table: Percentage distribution of combination feedings by age (Months 1-13)	New	Both

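### Month 3 has scheduled supplemental interviews but no combined-sample weight, so seven month-3 tables marked 'Both' cannot be weighted as labelled

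*Combined protocol and SAP*

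**What the plan says.** **Who is interviewed at month 3.** Section 1.2 says of the supplemental sample: "This sample will be interviewed at four key time periods (1 or 3, 7, 13, and 24 months". In Table 4-1 the row "Supplement Sample – Infant 6 wks-2.5 mos" has interviews at months 3, 7, 13 and 24 and none at month 1. The other two supplemental rows (prenatal, and infants under 6 weeks) have month 1 and no month 3. The text of Section 4.8 differs. It gives supplemental women enrolled after birth a 3-month interview, with a 1-month interview possible depending on the infant's age.

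**Why the group matters.** Section 4.6.3, step 5: "Only rare population subdomains such as black mothers and infant who have no prenatal WIC exposure will be eligible for the supplemental group".

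**Which weights exist.** Table 6-1 lists combined cross-sectional weights for months 1, 7, 13 and 24. The month-1 weights carry the restriction "Only prenatally recruited infants and infants recruited postnatally within the window for the 1-mo interview". Month 3 has "Month3CoreWgt", core only. Two other combined weights include the late-enrolled infants. HazardModelCombWgt needs at least one postnatal interview and is described as "Earliest weight that uses entire sample". CritWaveLongWgt has the condition "If postnatally recruited, after the 1-mo interview window responded at mos. 3, 7, 13, and 24".

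**Which outputs need one.** Seven rows of Table 7-2 use month 3 alone and are marked 'Both': responses to infant cues, additions to the formula bottle, pacifier use, reasons for pacifier use, foods before a spoon, workplace pumping accommodations, and "Average Edinburgh Postpartum Depression Scale score by breastfeeding status (Month 3").

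**The concern.** Section 6.2 promises weights for joint analyses of the two samples, and Section 7.5 says both will be used where possible. At month 3 an analyst given a 'Both' table has two routes.

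The first is the core weight, which leaves out interviews already collected from a group the supplement was designed to enlarge. The second is the total-sample base weight of Section 6.2, the core weight W_B divided by 1 + r. That weight is right only where the supplemental partners of the down-weighted core cases are also interviewed, and at month 3 most are not.

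At stake is precision for late-enrolled infants on the first route, and a distorted sample mix on the second.

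**Working it through.** **1. The plan's own weight figure.** Section 6.2 expects core weights on the order of 550. Its inputs give 2,000,000 × 0.78 / 2804 = 556, which agrees. The rest of the check is structural and disputes no stated figure.

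**2. Waves set side by side.** Under Table 4-1, supplemental interviews fall at months 1, 3, 7, 13 and 24. Combined cross-sectional weights in Table 6-1 fall at months 1, 7, 13 and 24. The difference is month 3 alone. Months 5, 9, 11, 15 and 18 also lack a combined weight, but no supplemental case is scheduled then.

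**3. Interviews set aside by the core weight.** For each core case in the late-enrolled group there are r supplemental cases. The share dropped is r/(1+r), and the group's standard error (SE) with both samples, relative to core alone, is 1/√(1+r). Clustering within sites is ignored.

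| r (assumed) | Share dropped | SE ratio | SE cut from using them |
|---|---|---|---|
| 1 | 50% | 0.707 | 29% |
| 0.5 | 33% | 0.816 | 18% |
| 0.25 | 20% | 0.894 | 11% |

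The documents give no r for this group. A rough average over all groups comes from Section 4.6: 80 × 55.4 = 4432 recruits, less 2804 core, leaves 1628 supplemental, so r averages 1628/2804 = 0.58. This assumes one-to-one alternation and equal consent, and that 55.4 counts both samples.

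**4. Effect on groups that are reported.** If late-enrolled infants make up a share f of the reported group, the SE ratio is √(1 − f + f/(1+r)).

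- All postnatal enrollees, f = 0.5 assumed: √0.75 = 0.866 at r = 1, a cut of 13%; √0.833 = 0.913 at r = 0.5, a cut of 9%.
- Whole sample, r = 1: f = 0.05 gives √0.975 = 0.987, a cut of 1.3%; f = 0.10 gives √0.95 = 0.975, a cut of 2.5%.

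**5. Why the Section 6.2 weight cannot be applied to everyone at month 3.** Under Table 4-1, supplemental cases recruited prenatally or under 6 weeks have no month-3 interview. Their core counterparts would carry W_B/(1+r) with no partner present, so their weighted total falls by the factor 1/(1+r): to 50% at r = 1 (weight 556/2 = 278) and to 63% at r = 0.58. Late-enrolled infants would be fully represented. Illustration: in an r = 1 domain that is 90% prenatal and 10% late (assumed), the prenatal weighted total halves from 0.90 to 0.45, and its share falls from 90% to 0.45/(0.45 + 0.10) = 82%.

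**6. Whether another listed weight can stand in.** HazardModelCombWgt is positive for anyone with at least one postnatal interview and rests on the same W_B/(1+r), so step 5 applies if it is used on a month-3 item. CritWaveLongWgt has the same feature and also requires response through month 24. Neither is a month-3 cross-sectional weight.

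**The case against.** The best defence is that the plan already lists a sound month-3 weight. The core sample covers the whole population, including core infants enrolled at 6 weeks to 2.5 months, so Month3CoreWgt introduces no bias. This stands. A reader might infer that the month-3 estimates will be biased, but the documents do not support that: nothing in them proposes the W_B/(1+r) weight for month-3 tables, and step 5 describes a misuse to be prevented. Even under that misuse, the nonresponse adjustment of Section 6.3 might restore part of the total, depending on the cells and on who counts as eligible.

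It can also be said that 'Both' is a loose label. Section 7.5 allows for data the supplement does not have, and rows such as self-feeding skills (months 9, 11, 13, 18) are marked 'Both' although months 9, 11 and 18 have no supplemental interview. This stands for multi-month rows, so only the seven month-3-only rows are counted. In those rows 'Both' can refer to no other month.

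A third stronger reading is that these infants are lost to early-feeding analyses altogether. They are not. Outputs marked 'Cumulative; Months 1, 3', such as breastfeeding initiation, and the survival models can use HazardModelCombWgt.

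Finally, no table shell reports infants enrolled at 6 weeks to 2.5 months separately; Table C-1 groups all who began postnatally. The 29% and 18% figures are therefore the most that could be gained at those values of r, and extra cases within the same 80 sites do not reduce between-site variance.

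**Conclusion.** The gap is real but moderate. Month 3 is the only wave with scheduled supplemental interviews and no combined cross-sectional weight, and seven tables are labelled as if one existed. With the listed core weight, estimates stay valid and the loss is precision: about 29% or 18% of the late-enrolled group's SE at r = 1 or 0.5, about 13% or 9% for all postnatal enrollees if half are late, and about 1 to 3% for whole-sample estimates at r = 1 with a late share of 5 to 10%. The values of r and both late shares are assumptions, and clustering is ignored. If the Section 4.8 text is right and supplemental infants under 6 weeks also have a month-3 interview, more interviews lack a weight and the gap is wider.

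**What to change.** 1. Reconcile the text of Section 4.8 with Table 4-1 on which postnatal supplemental enrollees have a month-3 interview.
2. Add Month3CombWgt, with replicates, to Table 6-1. Use W_B/(1+r) only for recruitment groups interviewed at month 3 in both samples, and W_B unchanged for all other core cases. Follow with the usual month-3 nonresponse adjustment.
3. Name this weight for the seven month-3-only 'Both' rows of Table 7-2, and state that HazardModelCombWgt serves the cumulative month-1-and-3 outputs and the survival models.
4. If the weight is not added, relabel the seven rows 'Core'.

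The cost is one more weight set and slightly more variable weights at month 3. No new data are needed.

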### ***Imputation***

Imputation will be used to adjust for item nonresponse, i.e., missing data for particular items among those who respond to a given wave. By using imputation to “plug holes” due to item nonresponse, we mitigate issues analysts would encounter in trying to analyze data with “swiss cheese” patterns of missingness. As with weighting, a carefully designed imputation procedure will reduce bias due to nonresponse (in this case, item nonresponse). Further discussion will be needed to identify the particular set of items to be imputed but this set should include, at a minimum, variables needed for weighting as well as key survey outcomes and covariates.

For imputation, Westat has created new software over the past decade called AutoImpute, which uses a cyclical n-partition hot deck (an approach analogous to the Gibbs sampler but using the hot deck to generate the imputations). (See Judkins 1997; Judkins et al. 2007; Judkins, Piesse, and

Krenzke 2008; and Krenzke and Judkins 2008.) This software is designed to facilitate preservation of multivariate distributions while also ensuring that imputations maintain skip patterns and adhere to constraints. We have used it successfully on about a dozen major surveys, including one with a baseline and eight followup interviews. With virtually any imputation procedure, if there are outliers and inconsistencies in the data, these can become magnified after imputation. For this reason, it is important to carefully edit the data prior to imputation. After imputation, the same analytic edits that we ran on the raw data will be run again on the imputed data. As part of this process, will need to examine and possibly deal with outliers that could affect imputation. Dealing with outliers might involve setting them to missing and imputing for the newly missing data or setting them to reasonable boundary values. This type of detail will be worked out in consultation with subject-matter experts and FNS.

## 6.4 Nonresponse Bias Analysis

To the extent that respondents are systematically different from the population as a whole with respect to characteristics used in an analysis, the potential for nonresponse bias exists. Statistical methods used to compensate for missing data (weighting and imputation) aim to reduce nonresponse bias. Since there is generally no way to directly measure the difference in key survey characteristics between respondents and the population as a whole, various methods have been developed that aim to assess the potential for nonresponse bias.

One approach we will use is to examine bivariate cross tabulations of data from one wave by response status at a followup wave to check for evidence of nonresponse bias at followup. Since there will be eight waves of followup on the core sample after the first interview for infants recruited after birth, and ten waves of followup on the core sample for those required prenatally, there will be many possible cross-tabs that could be run. By the 24-month interview, there will be thousands of measurements from prior waves that could be used to check for nonresponse bias at the 24-month interview. Obviously the scope of these tabulations could quickly become unmanageable. We will need to establish a few sentinel variables from early waves to use as benchmarks for first-degree bias estimation. We will work with FNS to arrive at a set of key variables to be used for this purpose.

As discussed above, the weighting class adjustments for nonresponse aim to reduce nonresponse bias. Thus, while the subgroup response rate analysis described above may be useful in identifying the *potential* for nonresponse bias due to varying response propensities among key subgroups, this

nonresponse bias may be mitigated through the adjustments for nonresponse. To examine this, we will compare unadjusted estimates (i.e., computed using weights that do not include the adjustment for nonresponse to the particular wave) to adjusted estimates.

With a longitudinal study such as WIC ITFPS-2, another technique that can be used is to compare prior-wave estimates for key statistics for respondents to the given wave to the corresponding prior-wave estimates computed using the full set of prior-wave respondents.

Another method that could be considered is benchmarking estimates from WIC ITFPS-2 to estimates from other sources, provided such external estimates are available. Although benchmarking to external estimates is a method commonly included in a repertoire of nonresponse bias analysis techniques, it is recognized that this approach does not allow for isolation of bias due to nonresponse. Besides nonresponse bias, differences between the survey estimates and external estimates might be attributable to temporal differences, differences in survey populations or survey measures, or other sources of error such as coverage bias.

## 6.5 Variance Estimation

Two broad classes of methods have been developed for computation of standard errors of estimates from complex sample surveys: (1) replication methods and (2) Taylor series linearization. The WIC ITFPS-2 data files will contain the information necessary for analysts to use either of these approaches to compute standard errors. Several software packages are available for the analysis of data from complex sample surveys using one or both of these approaches to variance estimation. These include WesVar, SUDAAN, the survey procedures in SAS, Stata, and the *Survey* package in R. Users of the RUF from this project will particularly appreciate the ease of use afforded by the combination of replicate weights and one of these packages.

